#### **8.6. Summary of sUA from screening to baseline, stratified by ULT at screening**

An additional baseline summary will be produced, stratifying all randomised individuals by whether they were on ULT at screening or not. A summary of sUA at screening and baseline (Day 0 pre-dose) will be summarized by treatment group, as well as the change in sUA from screening to baseline.

This document is confidential.

## 9. Efficacy

### 9.1. Assessment of sUA Time Curve and Summaries

The sUA time curve with assessments at Day 0, pre-treatment (0 h), Day 0, post-treatment (4.5 h), Day 7, Day 14, Day 21 and Day 28 in TP6 will be used to estimate the proportion of time that the sUA level is below 6 mg/dL by Day 28. Based on the serum samples collected during TP6 an estimate of the time with sUA < 6 mg/dL can be determined by connecting each two neighboring data points with a straight line. If the sUA time curve goes above 6 mg/dL the linear interpolation method will be used to estimate the point in time at which the SUA time curve intercepts the line between the last sUA value < 6 mg/dL and the first value  $\geq$  6 mg/dL. The proportion of time that the sUA level is < 6 mg/dL will be computed by taking the ratio between the time during which the sUA level remains < 6 mg/dL (if necessary, using the linear interpolation method) and the entire time interval within TP6 by Day 28, or the last available assessment before Day 28. Actual times will be plotted on the time curve, but only the interpolation of actual times up to Day 28 will be used. For example, if a patient had their Day 28 assessment on Day 30 then a straight line will connect Day 30 and their previous assessment, but the percentage of time the time curve is < 6 mg/dL will be derived only up to Day 28. If a point at Day 28 is not available on the curve (possibly due to an extension of TP6 for reasons such as presenting mild-moderate COVID-19 symptoms), then the next available assessment between Day 28 and up to, and including EOS will be used to interpolate the curve up to Day 28. This can include the use of unscheduled sUA assessments. However, note that no sUA assessments are scheduled for EOS as this is conducted via phone call. For example, if a patient is missing their Day 28 assessment, and the next assessment is at Day 40 of TP6 (e.g., once their mild-moderate COVID-19 resolve) then this additional timepoint will be plotted and a straight line will be connected between this and their previous assessment in TP6 prior to Day 28 (as Day 40 is now the next available assessment between Day 28 and up to, and including EOS) and the percentage of time the time curve is < 6 mg/dL will again be derived up to Day 28. If there are no such assessments available, but the use of unscheduled assessments allows the extension of the time curve from the last scheduled assessment prior to Day 28 then these can also be used. For example if a patient has all scheduled assessments during TP6 up to Day 21, with no assessments on or after Day 28, up to and including EOS, but has an unscheduled assessment on Day 25 then the percentage of time with sUA level < 6 mg/dL for TP6 would be taken to be the percentage of time the sUA levels were < 6 mg/dL from Day 0 to Day 25. If only 2 or fewer assessments are available (allowing for the use of assessments after Day 28 up to, and including EOS, and further unscheduled assessments prior to Day 28), and the first and last attended assessments are less than 7 actual days apart, then the response evaluation of Treatment Period 6 will be missing. Otherwise, the response evaluation will be derived from the available data points. For a patient to be considered a responder in TP6, the proportion of time that the sUA level is < 6 mg/dL (i.e., percentage of nonhyperuricemic time) during Treatment Period 6 by Day 28 (or last available assessment prior to Day 28 if no assessments are available from Day 28 up to, and including EOS) must be at least 80%.

For example, if a patient only has measurements on both Day 0 assessments and Day 8 (planned assessment for Day 7) then percentage of time with sUA level < 6 mg/dL for TP6 would be taken to be the percentage of time the sUA levels were < 6 mg/dL from Day 0 to Day 8. However, if the Day 7 planned assessment was taken on Day 6 then this patient would have a missing value for their response.

A frequency table of the percentage of responders in TP6 will be provided by treatment group in overall and stratified by tophus status at baseline for the ITT population. Additionally, a summary table with the total

This document is confidential.

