The sUA time curve with assessments at Day 0 pre-treatment (0 h), Day 0 post-treatment (4.5 h), Day 7, Day 14, Day 21, and Day 28 will be used to estimate the proportion of time that the sUA level is below 6 mg/dL. Based on the serum samples collected during Treatment Period 6, an estimate of the time with sUA < 6 mg/dL by Day 28 can be determined by connecting each two neighboring data points with a straight line. If the sUA time curve goes above 6 mg/dL the linear interpolation method will be used to estimate the point in time at which the sUA time curve intercepts the line between the last sUA value < 6 mg/dL and the first value \geq 6 mg/dL. The proportion of time that the sUA level is < 6 mg/dL will be computed by taking the ratio between the time during which the sUA level remains < 6 mg/dL (if necessary, using the linear interpolation method) and the entire time interval within Treatment Period 6 by Day 28, or the last available assessment before Day 28. Actual times will be plotted on the time curve, but only the interpolation of actual times up to Day 28 will be used. If a point at Day 28 is not available on the curve (possibly due to an extension of TP6 for reasons such as presenting mild-moderate COVID-19 symptoms), then the next available assessment between Day 28 and up to, and including EOS will be used to interpolate the curve up to Day 28. This can include the use of unscheduled sUA assessments. If there are no such assessments available, but the use of unscheduled assessments allows the extension of the time curve from the last scheduled assessment prior to Day 28 then these can also be used. If only 2 or fewer assessments are available (allowing for the use of assessments after Day 28 up to, and including EOS, and further unscheduled assessments prior to Day 28), and the first and last attended assessments are less than 7 actual days apart, then the response evaluation of Treatment Period 6 will be missing. Otherwise, the response evaluation will be derived from the available data points.

The proportion of time that the sUA level is < 6 mg/dL, i.e., percentage of non-hyperuricemic time, will be computed by taking the ratio between the time during which the sUA level remains < 6 mg/dL (if necessary, using the linear interpolation method) and the entire time interval within Treatment Period 6 by Day 28 (or last available assessment prior to Day 28 if no assessments are available from Day 28 up to, and including EOS).

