Appendix A Schedule of Assessments, continued

Assessment	Scr. - 45 d to D0 (Pre-dose) ³	Treatment Phase														EOS ¹	ET
		TP1 ²		TP2 ²		TP3 ²		TP4 ²		TP5 ²		TP6 ²					
Day	D0	D21	D0 ⁵	D21	D0 ⁵	D21	D0 ⁵	D21	D0 ⁵	D21	D0 ⁵	D7 ⁴	D14 ⁴	D21 ⁴	D28		
Tophus Assessment/Photography	X							X								X	X
Gout Flare Assessment ²²	X	X	X	X	X	X	X	X	X	X	X	X	X	X	X	X	X
Gout Flare Weekly Diary		Continuously on Weekly Basis ²³															X
Joint Assessment (tenderness, swelling)		X						X								X	X
Health Questionnaires ²⁴		X						X								X	X
Collect Sample for sUA	X	Refer to Schedule of Assessments (Appendix B) for sUA Sample Collection during Treatment Phase															X
PD/Uricase Activity Assessment		Refer to Schedule of Assessments (Appendix B) for PD/Uricase Activity Assessments during Treatment Phase															X
Study Drug Administration		Refer to Schedule of Assessments in Appendix B for Study Drug Administration during the Treatment Phase															
Infusion Reaction Follow-up		Refer to Section 12.2.1.5															
Concomitant Medications / Procedures		Continuously														X	X
AE Collection		Continuously														X	X
SAE Collection		Continuously														X	X

1. Phone call at 30 (+4) days after the last study drug infusion for assessment of concomitant medications/procedures, AEs, and SAEs.
2. Visit window at Day 21 of each Treatment Period is +2/-1 days; visit window at Day 7 and Day 14 of Treatment Period 6 is +2/-1 days; visit window at Day 28 of Treatment Period 6 is +3/-4 days.
3. Visit window is -2 days.
4. Assessments at this visit are permitted to be performed remotely (inclusive of collecting applicable lab draws and assessments per protocol visit windows).

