## 4. Endpoints

### 4.1. Primary Efficacy Endpoint

Each of the two active treatment groups, SEL-212A and SEL-212B, are compared to placebo with regards to the following primary endpoint:

- The percentage of patients who achieve and maintain reduction of sUA < 6 mg/dL for at least 80% of the time during Treatment Period 6 by Day 28

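### A final Treatment Period 6 sample on Day 24-27 is scored on a shortened denominator, while one on Day 29-31 is standardised to Day 28

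*SAP*

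**What the plan says.** The primary endpoint requires sUA below 6 mg/dL for "at least 80% of the time during Treatment Period 6 by Day 28" (SAP 4.1).

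The curve is built by straight lines between samples at Day 0 (pre-dose and 4.5 h), 7, 14, 21 and 28 of Treatment Period 6. SAP 9.1 works on the actual time scale: "Actual times will be plotted on the time curve, but only the interpolation of actual times up to Day 28 will be used". The denominator is "the entire time interval within TP6 by Day 28, or the last available assessment before Day 28"; Protocol 13.4.1 words it as "the entire time interval within Treatment Period 6 by Day 28, or the last available assessment before Day 28". SAP 9.1 limits the shorter interval to one case: "last available assessment prior to Day 28 if no assessments are available from Day 28 up to, and including EOS".

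The window comes from Protocol Appendix A, footnote 2, repeated in SAP Table A, footnote 2: "visit window at Day 28 of Treatment Period 6 is +3/-4 days". A compliant final visit can therefore be on any day from 24 to 31.

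SAP 9.1 gives a worked case on each side of Day 28:
- Final sample on Day 30: "the percentage of time the time curve is < 6 mg/dL will be derived only up to Day 28".
- Day 28 missed, unscheduled sample on Day 25: the result "would be taken to be the percentage of time the sUA levels were < 6 mg/dL from Day 0 to Day 25".

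No sUA is scheduled after the Day 28 visit, because the End of Study contact is a telephone call (SAP 9.1; Appendix A, footnote 1).

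**The concern.** Late and early final visits are treated differently. Late ones are brought back to a common 28 days. Early ones keep whatever length they happen to have, and the days lost are the last days of the dosing interval, where sUA is highest in a patient who is losing control. A patient with all six samples, none missing and none out of window, can then be classed by appointment day rather than by sUA.

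The plan's safeguards do not reach these patients. Multiple imputation and the tipping-point analysis (SAP 9.2) apply only to missing responses, and these responses are not missing. The rule that voids a response with two or fewer samples less than 7 days apart does not apply either. No planned sensitivity analysis concerns visit timing. The stopping rule covers Day 21 of Treatment Periods 1 to 5, so first loss of control in Treatment Period 6 is judged by the time curve alone.

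Mean Treatment Period 6 sUA, the basis of key secondary endpoints 1 and 2, is the area divided by the corresponding interval (SAP 9.1), so it has the same dependence.

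**Working it through.** **1. The plan's own cases.** The Day 30 case gives a denominator of 28 and the Day 25 case gives 25. So the denominator is min(28, V), where V is the actual day of the last sample.

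**2. Days below 6 mg/dL needed to respond = 0.8 × denominator.** Take a patient who crosses 6 once and stays above. Days below 6 equal the crossing day, so the class differs from that given by a Day 28 visit only in the last column.

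| V | Denominator | Days needed | Crossing days that change class |
|---|---|---|---|
| 24 | 24 | 19.2 | 19.2 to before 22.4 |
| 25 | 25 | 20.0 | 20.0 to before 22.4 |
| 26 | 26 | 20.8 | 20.8 to before 22.4 |
| 27 | 27 | 21.6 | 21.6 to before 22.4 |
| 28-31 | 28 | 22.4 | none |

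**3. Illustrative patients.** The documents give no individual curves, so these values are assumed.
- Curve 1: pre-dose 1.0, 4.5 h 0.1, Day 7 0.5, Day 14 2.0, Day 21 5.5, then +0.5 mg/dL per day. It crosses at 21 + (6 − 5.5)/0.5 = Day 22. V = 24: 22/24 = 91.7%, responder. V = 28: 22/28 = 78.6%, non-responder.
- Curve 2: Day 21 5.8, then +0.5 per day. It crosses at Day 21.4. V = 24, 25, 26: 89.2%, 85.6%, 82.3%, responder. V = 27: 79.3%, and V = 28-31: 76.4%, non-responder.
- Curve 3: Day 14 1.0, Day 21 6.9. It crosses at 14 + 7 × 5.0/5.9 = Day 19.93. V = 24: 83.1%, responder. V = 25: 79.7%, and V = 28-31: 71.2%, non-responder.
- No change: crossing at Day 19 (79.2% at V = 24, 67.9% at V = 28, both non-responder); crossing at Day 23 (95.8% and 82.1%, both responder); always above 6; always below 6.

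**4. Mean sUA, curve 1, linear trapezoid (4.5 h = 0.1875 day).**
- Area to Day 21: 0.103 + 2.044 + 8.750 + 26.250 = 37.147.
- V = 24: add 3 × (5.5 + 7.0)/2 = 18.750. Mean = 55.897/24 = 2.33.
- V = 28: add 7 × (5.5 + 9.0)/2 = 50.750. Mean = 87.897/28 = 3.14.
- Day 24 value carried to Day 28: (55.897 + 4 × 7.0)/28 = 3.00.

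**5. Effect on the test.** One patient is 1/47 = 2.1 points. The plan states about 90% power for 37% against 5% with 47 per arm at two-sided 2.5%. The continuity-corrected normal approximation gives 92.3%, consistent with that. The share of patients affected is not in the documents. Assumed gains of 1, 2 or 5 points in the active rate move power to 93.7%, 94.9% or 97.4%.

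**The case against.** The strongest case against is that the effect is narrow and probably rare. A class change needs a final visit on Day 24-27, no later sUA, and a lasting crossing within an interval of at most 3.2 days (22.4 − 19.2). Patients who met the stopping rule are already failures under the composite strategy, so the pool is mainly those controlled through Treatment Period 5. Protocol 7.6.3.2.1 reports that all 21 patients in Phase 2 cohorts 13, 15 and 17 who were controlled at week 12 stayed controlled through treatment period 5. With 0 of 21, the one-sided 95% upper limit for loss of control is 1 − 0.05^(1/21), about 13%, before the other two conditions apply. This stands, with the limit that those patients had five doses, not six.

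Two stronger readings are tempting, and the documents support neither.
- A reader might infer that any late rise passes with a Day 24 visit and fails with a Day 28 visit. It does not: a lasting crossing before Day 19.2 fails both, and one from Day 22.4 onward passes both.
- A reader might infer that the rule could produce a false positive. Treatment is randomised and blinded, and unblinding post-dose laboratory results go only to unblinded staff (Protocol 9.4), so visit day should not depend on arm. Without a drug effect, the rule acts alike on all arms.

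The 100%-of-time responder endpoint (SAP 9.3.3) is also unmoved by these changes, since a patient crossing between Day 19.2 and 22.4 fails it either way. That is a useful check, but it is not confirmatory and answers a stricter question. None of these objections supplies a rule that extends an early in-window curve to Day 28.

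**Conclusion.** The point holds in limited form. The asymmetry follows directly from the text: an in-window Day 24-27 sample with no later sUA lowers the required time by 0.8 to 3.2 days, while a Day 29-31 sample changes nothing. For patients who lose control late, the change can only be from non-responder to responder. With 5% response assumed on placebo, any net shift falls mainly on the SEL-212 arms and inflates the size of a real effect. The reverse is possible for a curve that starts high and then falls, because the days allowed above 6 drop from 5.6 to 4.8 when V = 24.

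This rests on a single lasting crossing, visit timing that is independent of arm, and no unscheduled sUA from Day 28 onward. How many patients are affected cannot be worked out from the documents. The effect on the primary test is probably small; the estimated responder difference and the two mean-sUA endpoints are where it would show. The sample size is untouched.

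**What to change.** Before unblinding, in SAP 9.1 and Protocol 13.4.1:
- For every Treatment Period 6 curve whose last sUA is on Day 24-27, scheduled or unscheduled, use a fixed 28-day denominator and carry the last observed sUA to Day 28 for responder status.
- Revise the SAP's Day 25 example to match, so that identical data are not scored differently by visit label.
- Apply the same rule to mean Treatment Period 6 sUA, and state that it is approximate there (3.00 against 3.14 for curve 1).
- Report the rule as now written as a sensitivity analysis.

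For a single upward crossing, the carry-forward settles responder status. If the last value is 6 or above, the crossing has already been seen and is divided by 28. If it is below 6, at least 24 days are already below, more than the 22.4 needed. Curve 1 sampled on Day 24 becomes 22/28 = 78.6%, the same as with a Day 28 visit.

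The visit window need not change. Changing it would require a protocol amendment with IRB/IEC approval (Protocol 15.3), would move a visit that also carries safety and questionnaire assessments, and would break the assessment timing shared with SEL-212/301.

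Cost: one rule, one revised example and one extra sensitivity table. The SEL-212 responder rate may be marginally lower, and carry-forward remains an assumption for the mean.

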**Statistical Analysis Plan**  
 Sponsor: Selecta Biosciences  
 Protocol No.: SEL-212/302

---

and percentage of time a patient has sUA values < 6 mg/dL in TP6 will be provided by treatment group in overall and stratified by tophus status at baseline for the ITT.

Summary table of the actual values and change from baseline (Day 0 TP1) for sUA results will be provided for each scheduled sampling time point by treatment group. Additionally, mean sUA level, reduction in mean sUA and percent reduction in mean sUA from baseline during TP6 will be presented by treatment group.

- Mean sUA level is defined as the area under the sUA time curve (computed using the linear trapezoidal rule during Treatment period 6) divided by the corresponding time interval.
- Reduction in mean sUA is computed by subtracting baseline sUA level from mean sUA during Treatment period 6.
- Percent reduction in the mean sUA from baseline is computed as the mean sUA level during Treatment period 6 minus baseline sUA level divided by baseline sUA level multiplied by 100

The sUA levels will be visualized in a box-plot by assessment time and treatment.

## 9.2. Analyses of Primary Efficacy Estimands

The statistical testing of each SEL-212 treatment group versus placebo in all four estimands will be performed using the Mantel-Haenszel (MH) estimate and test for common risk difference considering the randomization stratum of tophus presence (yes/no) with a two-sided type 1 error rate  $\alpha = 2.5\%$  to adjust for the two comparisons against placebo. Only the test results of the main estimand will be considered as confirmatory.

In addition, a logistic regression model will be fitted, with response as the outcome variable, tophus presence (yes/no) at baseline, treatment group included as covariates.

The analysis of all four estimands will be carried out based on the ITT population, and analyses on the main, second and third estimand will be performed, but the population will be each of the defined mITT populations, the PP and the all randomized set as opposed to the ITT. For missing response evaluation data in TP6 (see also Section 9.1) values will be multiple imputed. The logistic method considering the tophus status at baseline and the treatment group will be applied for the multiple imputation. For the main, second and fourth estimand of primary efficacy, sensitivity analysis will be performed using the tipping-point analysis for binary response, to investigate the sensitivity to departures from missing-at-random (MAR). For patients with missing response status, the underlying response probability will be varied systematically and comprehensively such that, should one exist, a tipping point can be identified where if the probability of being a non-responder in the treatment group is higher than in the placebo group, the statistical significance switches from treatment effect p-value  $<0.025$  to treatment effect p-value  $\geq 0.025$ . For each arm, the following scenarios will be explored, where the true underlying response probability amongst those with missing response status will have the following probabilities:

0.01, 0.11, 0.21, 0.31, 0.41, 0.51, 0.61, 0.71, 0.81, 0.91, 0.99.

The analysis will be performed in each combination of placebo probability to SEL-212 active treatment arm probability, with the most extreme cases being when one arm in the comparison has a response probability of 0.99 and the other has a response probability of 0.01. Once a tipping point has been established, scenarios that make the treatment effect more favorable to the placebo arm will not be examined. Responses for those with missing response data will be imputed multiple times for each scenario, with responses drawn with the probabilities listed above. In each scenario, the results across multiply imputed

This document is confidential.

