8.3 Patient Completion and Withdrawal Criteria

8.3.1 Screen Failures and Replaced Subjects

A patient is considered enrolled in the study at the time of ICF signature. Any patient that is screened but not dosed will be considered a screen failure and the reason for failure will be documented. Any patient that is randomized but not dosed will be replaced and not included in the ITT population, and the reason for not being dosed will be documented.

Within the 45-day screening window, out-of-range laboratory tests may be repeated up to 2 times before declaring a screen failure (except for COVID-19 testing as described in [Section 12.1.8.7](#)). After the 45-day screening window, patients can be re-screened once.

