### 5.3. Intent-to-Treat Set

The Intent-to-Treat (ITT) Set will include all randomized patients who were dosed. Patients will be analyzed according to randomized treatment group assignment. Replaced subjects will not be included in the ITT. The ITT will be used as primary population for analyses of efficacy endpoints.

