### 5.6. All randomized Set

The all randomized set will include all patients who were randomized. Patients will be analyzed according to randomized treatment group assignment.

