**Statistical Analysis Plan**

Sponsor: Selecta Biosciences

Protocol No.: SEL-212/302

population-level summary as in the main estimand, but with applying the treatment policy strategy in case of all intercurrent events (i.e. all month 6 assessments until Day 28 will be used even for patients who have discontinued the study drug) with exception of deaths, where the composite strategy will be used.

A third estimand for the primary efficacy endpoint is defined using the same population, variable and population-level summary as in the main estimand, but applying the composite strategy for all intercurrent events, i.e. all of the above listed events will be considered as treatment failures.

A fourth estimand for the primary efficacy endpoint is defined using the same population, variable and population-level summary as in the main estimand, but the intercurrent event handling of premature stopping of study treatment due to a positive COVID-19 test result along with severe or critical symptoms of COVID-19 will be handled according to the treatment policy strategy.

The main, second and third estimands will be repeated five times, once with the population changed to each of the three defined mITT populations, once with the population changed to the all randomized set, and once with the population changed to the PP set.

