### 7.2. Key Definitions

Baseline is defined as the last non-missing value prior to the start date and time of the study drug. For Health questionnaires (including HAQ-DI, SF-36, and PGA), gout flare assessment, tender joint assessment and swollen joint assessment, if no assessment is available prior to the start time of the study drug, assessments post the start of study drug but on the date of first study drug administration may be considered as Baseline. Tophus status at baseline in the study will be based on IRT.

Day 0 of Treatment Period 1 is defined as the first date of study drug administration.

Overall study day will be calculated as date of event/collection – first dose date of the study.

Study day within each treatment period will be calculated as date of event/collection – first dose date at each treatment period to be consistent with protocol which defines the day of dosing in each treatment period as day 0.

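### In the supportive All Randomized Set analysis, SEL-212 patients who were never dosed are imputed at about the response rate of dosed patients in their arm

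*SAP*

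**What the plan says.** **Who is in which set.** SAP 5.3: "The Intent-to-Treat (ITT) Set will include all randomized patients who were dosed". SAP 5.6: "The all randomized set will include all patients who were randomized", analysed by assigned arm. The difference between the two sets is the patients randomized but never dosed. SAP 3.6 allows randomization from Day -7 to Day 0, so there can be a gap in which this happens.

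**What happens to an undosed patient.** Protocol 8.3.1: "Any patient that is randomized but not dosed will be replaced and not included in the ITT population". The same section adds: "Any patient that is screened but not dosed will be considered a screen failure". The commitment in Protocol 8.3.3.1 to follow patients through TP6 is framed around patients who have been dosed.

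**Which analyses bring them back.** SAP 6.1 repeats the main, second and third primary estimands on other populations, among them "once with the population changed to the all randomized set". SAP 6.2.5 does the same for both estimands of key secondary 5 (the responder endpoint in patients with tophi).

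**How a missing response is handled.** SAP 9.2: "For missing response evaluation data in TP6 (see also Section 9.1) values will be multiple imputed". It then names the model: "The logistic method considering the tophus status at baseline and the treatment group will be applied for the multiple imputation". SAP 9.3.2.5 uses treatment group alone for key secondary 5. An undosed patient has both covariates, because "Tophus status at baseline in the study will be based on IRT" (SAP 7.2).

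**Which events count as failure.** For the main estimand, SAP 6.1 lists the stopping rule, stopping treatment for an adverse event or for severe or critical COVID-19, death, and prohibited medication that significantly lowers sUA. A closing catch-all sends every other event to treatment policy, that is, to the observed TP6 values.

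**Status.** Protocol 13.4.1 calls the All Randomized repeat supportive. SAP 9.2 makes only the main-estimand test confirmatory.

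**The concern.** The ITT set here drops patients after randomization and replaces them. The three modified ITT sets and the per-protocol set also require dosing, so the All Randomized Set is the only planned population that keeps everyone randomized. Pre-dose losses cannot simply be assumed to be independent of arm: under Protocol 9.4 an unblinded site representative prepares study drug on the day of treatment and an unblinded nurse gives it.

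If the undosed patients return only to be given a response drawn from dosed patients with the same treatment label, the analysis says almost nothing about the effect of excluding them. A patient assigned to SEL-212 who received neither component is treated as though the drug had been given. At stake is the information in a supportive estimate, not the trial's primary conclusion.

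**Working it through.** **1. The plan's own figures.** Inputs from SAP 3.5: 45% versus 5%, two-sided alpha 2.5% per comparison, power 90%, continuity-corrected chi-square.

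- Uncorrected: n' = [2.2414·√(2·0.25·0.75) + 1.2816·√(0.45·0.55 + 0.05·0.95)]² / 0.40² = 26.7, so 27 per arm.
- Corrected: (n'/4)·[1 + √(1 + 4/(0.40·n'))]² = 31.5, so 32 per arm. This matches the plan.
- With 8% early termination: 32/0.92 = 34.8, so 35 per arm. This also matches.
- The later increases bring the target to 47 dosed per arm, used below.

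**2. Following one undosed SEL-212 patient through the rules.**

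- The patient is a screen failure under Protocol 8.3.1, so no TP6 sUA is expected and the response is missing under SAP 9.1.
- Never being dosed is not among the named failure events in SAP 6.1. If it falls under the catch-all, treatment policy asks for TP6 values that do not exist.
- In the main and second estimands the patient therefore goes to imputation, with a probability fitted to dosed patients.

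**3. Rate assigned by the imputation model.** The logistic model (tophus status plus treatment) was simulated with 47 dosed and 3 undosed per arm, 60% with tophi and 20 imputations. In 365 of 400 replicates the model could be fitted and every arm had at least one responder.

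- True rates 45/45/5%: mean imputed probability for undosed patients 0.450 and 0.451 in the SEL-212 arms, 0.066 in placebo.
- True rates 37/37/5% (37% is the reduced active rate in SAP 3.5): 0.374, 0.380 and 0.067.

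Each undosed SEL-212 patient thus adds about 0.45 of a responder at the planning rate. The difference as written stays near 40 points. With 5 undosed per arm, placebo is (2.35 + 5·0.066)/52 = 5.15%, so the difference is 45.0 − 5.15 = 39.8.

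**4. The same set with undosed patients as non-responders.** The documents give no never-dosed count, so k per arm is an assumption. Difference = (p₁ − 0.05)·47/(47 + k).

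| k undosed per arm | Share of arm | 45% vs 5% | 37% vs 5% |
|---|---|---|---|
| 1 | 2.1% | 18.8/48 = 39.2 | 15.04/48 = 31.3 |
| 2 | 4.1% | 18.8/49 = 38.4 | 15.04/49 = 30.7 |
| 3 | 6.0% | 18.8/50 = 37.6 | 15.04/50 = 30.1 |
| 5 | 9.6% | 18.8/52 = 36.2 | 15.04/52 = 28.9 |

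As written, the differences are about 40 and 32 points.

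**5. Uneven losses, k = 5 in one arm only, 45% vs 5%.**

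- One SEL-212 arm: 21.15/52 = 40.7%, less 5.0%, gives 35.7 points.
- Placebo: 45.0% less 2.35/52 = 4.5% gives 40.5 points.

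Non-responder coding can therefore move the estimate either way, while the written rule holds it near 40.

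**6. Effect on significance.** With non-responder coding and k from 1 to 5 per arm, power (uncorrected test) is about 99% at 45% and about 95% at 37%.

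**The case against.** **It is only a supportive analysis.** This stands. A reader might infer that the primary result is biased. It is not: the confirmatory test uses the ITT set, which contains no undosed patients.

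**The third estimand may already solve it.** That estimand makes all the events listed above it failures, and the list ends with the catch-all. Read that way, a never-dosed patient is a failure. One might instead infer that even the third estimand credits undosed patients with response, since never being dosed is not named. The text settles neither reading, so the point is firm only for the main and second estimands.

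**An existing rule may cover them.** Protocol 13.1, SAP 3.5 and the paragraph after the list in SAP 6.1 describe the version 6.0 estimand as counting patients who missed every TP6 sUA as failures. That would remove the problem. But these passages give the history of the sample size. The current event lists in SAP 6.1 and Protocol 13.4.1 do not contain the rule, and SAP 9.2 imputes.

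**The tipping-point analysis reaches response probabilities of 0.01.** This is partial cover. It is planned for the main, second and fourth estimands, is not said to extend to the All Randomized Set, and applies one probability to all missing patients in an arm, dosed or not.

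**The purpose is inferred, and the number may be tiny.** Both are fair. The documents nowhere say that this analysis exists to test the exclusion of undosed patients. Randomization on Day 0 is allowed, so there may be very few; with one per arm the effect is 0.8 points.

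**The counts will be visible anyway.** Largely so. SAP 8.1 tabulates both sets and lists screen failures with reasons, so no extra table is needed.

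**Conclusion.** The point holds in a limited form. In the All Randomized repeats of the main and second primary estimands, and of key secondary 5, the written rule credits undosed SEL-212 patients with about the response rate of dosed patients in their arm. The result largely restates the ITT estimate.

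Relative to non-responder coding, the overstatement is about 0.8 points (40 against 39.2) with one undosed per arm and 3.8 points (40 against 36.2) with five. This rests on 47 dosed per arm, the planning rates of 45% and 5%, an assumed number of undosed patients, and the reading that screen failures contribute no TP6 sUA. At the planned effects a change in significance is unlikely. The documents do not support any stronger claim, whether that the confirmatory test is affected or that the third estimand definitely has the same fault.

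**What to change.** Add to SAP 9.2 and 9.3.2.5: *In All Randomized Set analyses, patients randomized but never dosed are counted as non-responders and are not imputed.* State that this applies to the main, second and third primary estimands, which also settles the ambiguity in the third.

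Reconcile the new sentence with Protocol 13.1, SAP 3.5 and SAP 6.1, by saying whether the version 6.0 rule for patients with no TP6 sUA is still in force.

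Key secondaries 1 and 2 (mean sUA change) are also repeated on this set, with imputation by tophus status and treatment group (SAP 9.3.2.1 and 9.3.2.2). If these repeats are kept, undosed patients should not be imputed from the active arm; placebo-based multiple imputation is one option. Assigning zero change from a pre-randomization value is not advised: it is a single fixed imputation that understates variance, and that value may have been taken on urate-lowering therapy. SAP 7.2 ties baseline to the start of study drug, so a baseline for undosed patients must be defined as well.

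The cost is a sentence or two in the SAP and a few lines of code. The supportive estimate will usually be slightly less favourable.
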